6.2.1 Extended Exposure Period

Subjects will be instructed to use exclusively the product they were randomized to in the original study (THS 2.2 arm or CC arm) from check out of V10 until check out of V16. The use of THS 2.2 and CC will be allowed on site based on arm allocation. At the check-out of each ambulatory visit, subjects in the THS 2.2 arm will be instructed to continue using exclusively THS 2.2 until the check-out of V16.

For subjects in the THS 2.2 and CC arms, the use of other tobacco/nicotine containing products will be allowed including during the visits. However, for subjects in the CC arm, the use of THS 2.2 will not be allowed.

From V10 to V15, enrolled subjects in the THS 2.2 arm will be provided with a sufficient amount of THS Tobacco Sticks to cover their needs until the next visit; they will be requested to bring back THS 2.2 components including the unused and partially used packs of THS Tobacco Sticks at each ambulatory visit.

Any subject, who wants to make a quit attempt from using tobacco-containing products (e.g. THS 2.2 and CC) during the study will be encouraged to do so and will be referred to appropriate services. The subject will not be discontinued from the study, will come to all scheduled visits for assessments, and his/her financial compensation will not be affected. Subjects in the THS 2.2 arm who decide to quit using tobacco-containing products (e.g. THS 2.2 and CC) will not be provided with THS 2.2 anymore, starting from the day they intend to quit onwards.

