**Table 1: Actual Product Use General Pattern Categories**

Category Label	General Description
Dual-use	
 
• <math>\geq 1</math> THSts or CC and
 
• <math>1\% \leq</math> THSts <math>< 70\%</math> over the entire analysis period or
 
• THS-use and CC-use don't apply due to <math>< 50\%</math> of the days
 

CC-use	
 
• <math>\geq 1</math> THSts or CC and
 
• <math>< 1\%</math> THSts over entire analysis period and
 
• <math>< 1\%</math> THSts on <math>\geq 50\%</math> of the days in analysis period
 

Other-use	General category encompassing subjects with missing product use, or subjects using e-cigarettes or other tobacco products, subjects who quit, or subjects who switched across different use patterns between consecutive analysis periods.

Details of the product use categories are reported in Appendix 16.3 "Data Handling and Derivation of Product Use Pattern Categories". THSts = THS Tobacco Stick; THS=Tobacco Heating System; CC= Conventional Cigarette.

Full details of the product use categories derivation are reported in Appendix 16.3 "Data Handling and Derivation of Product Use Pattern Categories".

General product use categories will be used for both safety summaries and non-safety analysis. More granular product exposure categories will be used for the detailed description of the product use patterns observed in the study.

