### 16.3.2 Derivation of Actual Product Use Categories

Per-Day product use categories will be derived for each study day as indicated in Table 19, and the percent of days (over the whole analysis period) the subjects fall in each category will be computed.

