**Table 19: Per Day Actual Product Use Pattern Categories**

Category Label	Definition
THS-use	$nTHS + nCC \geq 1$ and $nECig/(nTHS+nCC+nECig+nOtherTob) < 50\%$ and $nOtherTob/(nTHS+nCC+nECig+nOtherTob) < 50\%$ and $nTHS/(nTHS + nCC) \geq 70\%$
Dual-use	$nTHS + nCC \geq 1$ and $nECig/(nTHS+nCC+nECig+nOtherTob) < 50\%$ and $nOtherTob/(nTHS+nCC+nECig+nOtherTob) < 50\%$ and $1\% \leq nTHS/(nTHS + nCC) < 70\%$
CC-use	$nTHS + nCC \geq 1$ and $nECig/(nTHS+nCC+nECig+nOtherTob) < 50\%$ and $nOtherTob/(nTHS+nCC+nECig+nOtherTob) < 50\%$ and $nTHS/(nTHS + nCC) < 1\%$
ECig-use	1) $nTHS + nCC \geq 1$ and $nECig \geq nOtherTob$ and $[nECig/(nTHS+nCC+nECig+nOtherTob) \geq 50\%$ or $nOtherTob/(nTHS+nCC+nECig+nOtherTob) \geq 50\%]$ ; or 2) $nTHS + nCC < 1$ and $nECig \geq nOtherTob$ and $(nECig \geq 1$ or $nOtherTob \geq 1)$
OtherTobacco-use	1) $nTHS + nCC \geq 1$ and $nECig < nOtherTob$ and $[nECig/(nTHS+nCC+nECig+nOtherTob) \geq 50\%$ or $nOtherTob/(nTHS+nCC+nECig+nOtherTob) \geq 50\%]$ ; or 2) $nTHS + nCC < 1$ and $nECig < nOtherTob$ and $(nECig \geq 1$ or $nOtherTob \geq 1)$
Abstainer	$nTHS + nCC < 1$ and $nECig < 1$ and $nOtherTob < 1$
Missing	Missing product use data

Note: nTHS, nCC, nECig, nOtherTob indicates the quantity of daily product use reported respectively for THS 2.2, CC, E-cigarette, and other tobacco..

The product use categories for the 3-month analysis periods (J[V4, V7], J[V7, V10], [V10, V13], J[V13, V16]) are derived following the same rules defined for per-day categories in Table 19, but using the average product use over the 3-month period. In addition:

- In order to factor in the higher relevance of later product use in the period for their impact on the endpoints, a weighted average approach is adopted, using the day number as weighting factor. The day numbers will be relative to the analysis period (i.e. weights ranging between 1 and the last day number of the period, normalized to

the total sum of the weights).

- THS-use or CC-use categories will be assigned to the analysis period when consistently observed on a per-day basis over the same period. In particular the frequency of THS-use and of CC-use per-day categories is calculated using the same weighting scheme previously adopted to compute the average product use over the entire 3-month period. THS-use and CC-use product use categories would be turned into Dual-use category if the weighted percent of days in respectively THS-use and CC-use is less than 50% during the analysis period.

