- Subjects in the THS-use category will be flagged as Exclusive-use if  $n_{\text{THS}}/(n_{\text{THS}} + n_{\text{CC}}) \geq 95\%$ . Subjects in CC-use will be flagged as Exclusive-use if  $n_{\text{THS}}/(n_{\text{THS}} + n_{\text{CC}}) \leq 5\%$ .
- Setting to Missing the product use categories if, after the interpolation, more than one third of the days (e.g. 30 days for the 3-month periods) of missing product use category during the analysis period. For the sensitivity analysis on missing product use data (see Section 12.7.1.3.4), the non-imputed product use category will be defined based on the available data (i.e. categories will be set to Missing only if no data is recorded for the analysis period).

The product use categories for the six-month ]V4,V10[ and [V10,V16[ analysis periods are derived following the same approach used for the 3-month periods, with the following differences:

- A weighting scheme for the calculation of the average of the product use over the 6-month period is adopted so to reflect the increasing relevance of the product use over time for their association with the value of the endpoints at the end of the period and especially during the last 3 months. To this aim, before being normalized the weights are set as follows:
  - Set to 1.0 for the ]V4, V7] and [V10, V13] parts of each 6-month analysis period
  - Range between 1.0 up until the last study day relative to the ]V7, V10[ and ]V13, V16[ time window, for the last 3-months of each 6-month analysis period.
- For each 6-month period, subjects having product use categories different between the two 3-months period components will move to a category with label “Switcher” if:

- Category is THS-use in one 3-month sub-period, and different from Dual-use (either CC-use or Other-use) in the other sub-period
- Category is CC-use or ECig-use or OtherTobacco-use or Abstainer in only one of the 3-month sub-periods
- For analysis purposes, an over-arching category with label “Other-use” will be used to incorporate all product use categories different from THS-use, Dual-use, or CC-use. The detailed categories will be used only for the descriptive summaries of the product use over time.
- Setting to Missing the category if at least one of the categories derived for the two 3-month sub-periods is missing, apart from:
  - If ]V7, V10[ category is Missing when the subjects early terminate after V7 and category of ]V4, V7[ is not missing, the latter will be assigned to ]V4, V10[.

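### SAP 16.3.2 labels THS-arm subjects who smoked no cigarettes and quit late in a 6-month period as Dual-use, while CC-arm subjects quitting on the same days go to Other-use

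*SAP*

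**What the plan says.** - **Quitters stay in the study.** Protocol 6.2.1 encourages quit attempts and says of such a subject: "The subject will not be discontinued from the study, will come to all scheduled visits for assessments". Quitters therefore contribute V16 samples.
- **Stated destination.** The Other-use row of SAP Table 1 covers "subjects who quit, or subjects who switched across different use patterns between consecutive analysis periods". Protocol Table 7 says the same.
- **Period category.** SAP 16.3.2 applies the per-day rules of Table 19 to each quarter, "but using the average product use over the 3-month period", with later days counting more ("using the day number as weighting factor"). A quarter is Abstainer only if its weighted average is below 1 unit/day for THS sticks plus cigarettes, for e-cigarettes and for other tobacco.
- **Days test.** A THS-use or CC-use period "would be turned into Dual-use category if the weighted percent of days in respectively THS-use and CC-use is less than 50" per cent. The denominator includes abstinent days: "the percent of days (over the whole analysis period) the subjects fall in each category will be computed".
- **Combining quarters.** One route to Switcher is "Category is THS-use in one 3-month sub-period, and different from Dual-use" in the other sub-period, so THS-use with Dual-use is exempt. CC-use in only one of the two quarters is always a Switcher. Table 20 carries both results to 12 months, and Switcher is analysed as Other-use.
- **Quit record.** A reported quit affects adherence and the PP population (SAP 6.3.3 and 10.3). No step of 16.3.2 uses it.

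**The concern.** A THS-only user who quits still has an average that is 100% THS, so the quarter starts as THS-use. If abstinent days then outweigh use days, the only label available is Dual-use, although no cigarette was smoked. The equivalent quit in the CC arm ends in Other-use, because the Switcher rule exempts THS-use with Dual-use but not CC-use with Dual-use. The arm difference comes from these two rules together.

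Dual-use versus CC-use is estimated in the FAS-EX for the smokers' health profile with p-values (SAP 12.7.1.3.3). It is also tested at 5% for exposure and nicotine markers (12.7.2.2, 12.7.2.3) and for lung and cardiovascular markers (12.7.2.4.1). Protocol Table 1 gives reversal after cessation within 1-7 days for COHb, 1-2 weeks for 8-epi-PGF2α, 2-4 weeks for 11-DTX-B2 and 4 weeks for sICAM-1. A subject abstinent for four weeks or more would tend to show cessation-level values of these markers while counted as a dual user. For a single sustained quit, only THS-arm subjects enter Dual-use this way, so the error makes dual use look more favourable.

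**Working it through.** The plan states no figure to reproduce. The check applies SAP 16.3.2 as written to a simple subject.

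**Inputs**
- From the SAP: day-number weights within a quarter. For six months, weight 1 in the first quarter, then 1 up to the last day number in the second. Also the Switcher rules and Table 20.
- Quarter length of 91 days, approximately V13 to V16 in SAP Table 17.
- Assumed: constant use of the allocated product only, zero use of everything after quitting, and zeros entered in the diary. Prior use is 15/day, with 10 and 20 as a range; the documents give no on-study rate.
- k is the number of days of use in ]V13, V16[ before quitting, so abstinent days at V16 are 91 − k.

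**Step 1: when is the last quarter Abstainer?** The weights sum to 91 × 92 / 2 = 4186. Abstainer requires 15 × [k(k+1)/2] / 4186 < 1, that is k(k+1) < 558.1. At k = 23 the product is 552 and at k = 24 it is 600, so Abstainer holds for k ≤ 23. At 10/day the limit is 837.2, so k ≤ 28; at 20/day it is 418.6, so k ≤ 19.

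**Step 2: days test on the last quarter.** It fails when k(k+1)/2 < 4186/2 = 2093. At k = 64 the sum is 2080 and at k = 65 it is 2145, so it fails for k ≤ 64, which is 27 or more abstinent days. This does not depend on the daily rate.

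**Step 3: days test on the 6-month period, weighted.** The total weight is 91 + 4186 = 4277. The test fails when 91 + k(k+1)/2 < 2138.5. At k = 63 the left side is 2107 and at k = 64 it is 2171, so it fails for k ≤ 63, which is 28 or more abstinent days.

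**Step 4: combine at 15/day, first six months in the allocated category, quit in the last quarter**

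| Abstinent days at V16 | THS arm, zero cigarettes | CC arm, zero THS sticks |
|---|---|---|
| 68 or more | Switcher (Other-use) | Switcher (Other-use) |
| 28 to 67 | **Dual-use** | Switcher (Other-use) |
| 27 | THS-use | Switcher (Other-use) |
| 0 to 26 | THS-use | CC-use |

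The Dual-use window is 28-62 days at 10/day and 28-71 at 20/day. On the exact nominal days of Table 17 the last quarter has 90 days; the 15/day window is unchanged and the other two end at 61 and 70. Quits earlier in the second six months go to Other-use in both arms.

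**Step 5: the first six months.** The ]V4, V10[ category, used through Month 6, behaves the same way. At 15/day on nominal days, THS-arm last use on days 115-154 (28-67 abstinent days at V10) gives Dual-use. CC-arm last use on days 115-155 gives Switcher.

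**The case against.** **Scope.** The window is narrow. It needs an abrupt, complete quit late in a 6-month period, no replacement by e-cigarettes or other tobacco, and zeros recorded. A quitter who leaves more than a third of the quarter's diary missing is set to Missing, which Table 1 also places in Other-use. A reader might infer that the algorithm mislabels quitters in general; it does not.

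**Table 1 is not one-sided.** Its Dual-use row repeats the 50%-of-days fallback and the table defers to Appendix 16.3, so 16.3.2 does implement one row. This stands. The two rows overlap without a rule of precedence, and both must be changed.

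**Primary contrast.** A reader might infer bias in THS-use versus CC-use. Subjects mislabelled Dual-use leave that contrast just as they would under Other-use. Recent quitters, up to 27 abstinent days in the THS arm and 26 in the CC arm, stay in both groups almost symmetrically, and the PP analysis excludes quit attempts. PP offers no such check on Dual-use.

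**Weighting.** The window depends on weighting the 6-month days test. The SAP spells out 6-month weights for average use but says the approach follows the 3-month one, where the days test shares the weights, so weighting is the natural reading. Unweighted, the same THS-arm quitters would be THS-use, which is not Other-use either.

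**Objective 9.** The SAP addresses it through the propensity-score analysis on the FAS-AR (12.7.3.2), which this relabelling leaves alone. The Dual-use contrasts are supportive or secondary, with no formal hypotheses. The product-use cross-tabulation in 12.7.2.1 has a below-1 cigarette category and could reveal such subjects, but it does not correct the estimates.

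**Conclusion.** The point holds in a limited form. Followed literally, 16.3.2 gives Dual-use to THS-arm subjects with no cigarettes who are 28-67 days abstinent at the end of a 6-month period (15/day, weighted 6-month days test). It gives Other-use to CC-arm subjects with the same quit. The first label contradicts the Other-use row of Table 1.

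The consequence is confined to the supportive and secondary Dual-use versus CC-use contrasts and the category-based summaries at V7, V10 and V16. A reader might want a percentage shift in, say, the Dual-use COHb mean. The documents do not support one: the number of quitters, the size of the Dual-use group and the COHb ratio between quitters and other dual users are all absent. The direction, towards a more favourable picture of dual use, follows for fast-reversing markers measured after the quit. The correction is worth making before database lock because it is cheap and the rule is clear.

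**What to change.** 1. In SAP 16.3.2 and the Dual-use row of Table 1, let a failed days test give Dual-use only if the period contains actual use of both products: at least one per-day Dual-use day, or days of both THS-use and CC-use. If it fails only because of Abstainer, ECig-use or OtherTobacco-use days, assign Other-use, in both arms. A subject with real dual-use days plus some abstinent days stays Dual-use. Rerunning the working with this rule gives Other-use from 27 abstinent days in both arms, so the one-day difference between arms also disappears.
2. For more recent quitters who stay in THS-use or CC-use, leave the primary classification as it is. It remains the relevant exposure for slower endpoints such as FEV1 and WBC (6-12 months in Protocol Table 1). Add a sensitivity analysis of COHb, 8-epi-PGF2α, 11-DTX-B2 and sICAM-1 that excludes subjects with a recorded quit and unbroken abstinent diary days up to V16.

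Cost: a SAP amendment, a small change to the derivation code, and one added table, all from diary and quit data already collected. A few subjects move to Other-use. The 6-month categories may differ slightly from those in the original study's analysis, which SAP section 9 wanted to match; the report should state how many subjects change.

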**Table 20: Overall Product Use Pattern Categories**

1 st /2 nd 6-month Product use	THS-use	CC-use	Dual-use	ECig-use	OtherTobacco-use	Abstainer	Switcher
THS-use	THS-use	Switcher	Dual-use	Switcher	Switcher	Switcher	Switcher
CC-use	Switcher	CC-use	Switcher	Switcher	Switcher	Switcher	Switcher
Dual-use	Dual-use	Switcher	Dual-use	Switcher	Switcher	Switcher	Switcher
ECig-use	Switcher	Switcher	Switcher	ECig-use	Switcher	Switcher	Switcher
OtherTobacco-use	Switcher	Switcher	Switcher	Switcher	OtherTobacco-use	Switcher	Switcher

Abstainer	Switcher	Switcher	Switcher	Switcher	Switcher	Abstainer	Switcher
Switcher	Switcher	Switcher	Switcher	Switcher	Switcher	Switcher	Switcher

Row and columns indicates the product use categories during the first and second six months analysis periods

- For subjects who do not enroll into the extension study, or for subjects who early terminate after V10 and category is missing for the period [V10, V16[, the product use category from ]V4,V10[ will be assigned for the product use category of the 12-month randomized period.
- For analysis purposes, an over-arching category with label “Other-use” will be used to incorporate all product use categories different from THS-use, Dual-use, or CC-use. The detailed categories will be used only for the descriptive summaries of the product use over time.
- Setting to Missing the category if at least one of the categories derived for the two 6-month analysis periods is missing, apart from the subjects who early terminate after V10 and category of first 6-month period is not missing.  
For the sensitivity analysis on missing product use data (see Section 12.7.1.3.4), the category will be set to Missing only if the categories of both the two 6-month periods are set to missing, otherwise the category will be set to the non-missing category of the two 6-month periods.

## 16.4 Tables, Listings, and Figures

The table below reports all the TFLs and flags those required for topline review, safety reporting, and Clinical Trial.gov reporting.

### Tables

Table No.	Title	Topline (Y/N)	Safety (Y/N)	Clinical Trial.gov (Y/N)
Table 15.2.1.1	Summary of Subject Disposition – Screened Subjects	Y		Y
Table 15.2.1.2	Summary of Reasons for Discontinuations – Enrolled Subjects			
Table 15.2.1.3.1	Summary of Protocol Deviations – Randomized Population			
Table 15.2.1.3.2	Analysis Sets and Reasons for Exclusions from Analyses – Screened Subjects			
Table 15.2.1.4.1	Summary of Demographics and Other Baseline Characteristics by 12-Month Product Use Categories – FAS-EX	Y		Y
Table 15.2.1.4.1.1	Summary of Demographics and Other Baseline Characteristics by 12-Month Product Use Categories and by Sex – FAS-EX			
Table 15.2.1.4.1.2	Summary of Demographics and Other Baseline Characteristics by 6-Month Product Use Categories – FAS-EX			Y

Table No.	Title	Topline (Y/N)	Safety (Y/N)	Clinical Trial.gov (Y/N)
Table 15.2.1.4.1.3	Summary of Demographics and Other Baseline Characteristics by 6-Month Product Use Categories – FAS-EX Subjects who Enrolled into Extension Study			
Table 15.2.1.4.1.4	Summary of Demographics and Other Baseline Characteristics by 12-Month Product Use Categories – FAS-EX Subjects who Enrolled into Extension Study			
Table 15.2.1.4.2.1	Summary of Demographics and Other Baseline Characteristics – Safety Population			
Table 15.2.1.4.2.2	Summary of Demographics and Other Baseline Characteristics – PP Population			
Table 15.2.1.4.2.3	Summary of Demographics and Other Baseline Characteristics – FAS-AR			
Table 15.2.1.4.3.1	Summary of Baseline Covariates Comparability for Smokers' Health Profile Analysis by 6-Month Product Use Categories – FAS-EX	Y		
Table 15.2.1.4.3.2	Summary of Baseline Covariates Comparability for Smokers' Health Profile Analysis by 12-Month Product Use Categories – FAS-EX			
Table 15.2.1.4.4	Summary of Baseline Covariates Comparability by Enrollment to			

Table No.	Title	Topline (Y/N)	Safety (Y/N)	Clinical Trial.gov (Y/N)
	Extension Study – FAS-EX			
Table 15.2.1.5	Summary of Medical History – Safety Population			
Table 15.2.1.6	Summary of Concomitant Diseases – Safety Population			
Table 15.2.2.1.1	Summary of Average Daily Product Use in Randomized Exposure Period by 12-Month Product Use Categories – FAS-EX			
Table 15.2.2.1.1.1	Summary of Average Daily Product Use in Randomized Exposure Period by 12-Month Other-use Detailed Categories – FAS-EX			
Table 15.2.2.1.1.2	Summary of Average Daily Product Use in Randomized Exposure Period by 12-Month Product Use Categories and by Sex - FAS-EX			
Table 15.2.2.1.1.3	Summary of Average Daily Product Use in Randomized Exposure Period by 12-Month Product Use Categories and by Consumption Level - FAS-EX			
Table 15.2.2.1.1.4	Summary of Average Daily Product Use in Randomized Exposure Period by 6-Month Product Use Categories – FAS-EX			
Table 15.2.2.1.2	Summary of Average Daily Product Use in Randomized Exposure Period – PP Population			

Table No.	Title	Topline (Y/N)	Safety (Y/N)	Clinical Trial.gov (Y/N)
Table 15.2.2.1.3	Summary of Average Daily Product Use in Randomized Exposure Period by Product Use – Safety Population			
Table 15.2.2.1.3.1	Summary of Average Daily Product Use by Arm – Safety Population			
Table 15.2.3.1	Covariates included in Analysis of Smokers’ Health Profile	Y		
Table 15.2.3.1.1	Analysis of Smokers’ Health Profile – FAS-EX	Y		Y
Table 15.2.3.1.2	Missing Product Use Sensitivity Analysis of Smokers’ Health Profile – FAS-EX			
Table 15.2.3.1.3	Sensitivity Analysis of Smokers’ Health Profile for Subjects Enrolled into Extension Study – FAS-EX			
Table 15.2.3.1.4	Multiple Imputation Sensitivity Analysis of Smokers’ Health Profile – FAS-EX			
Table 15.2.3.1.5	Sensitivity Analysis of Smokers’ Health Profile Derived Endpoints Including LLOQ Values in Denominator – FAS-EX			
Table 15.2.3.2.1	Supportive Analysis of Smokers’ Health Profile – FAS-EX	Y		

Table No.	Title	Topline (Y/N)	Safety (Y/N)	Clinical Trial.gov (Y/N)
Table 15.2.3.2.2	Supportive Analysis of Smokers' Health Profile – PP Population			
Table 15.2.3.2.3	Supportive Analysis of Smokers' Health Profile – FAS-AR			
Table 15.2.3.3.1	Secondary Analysis of Biomarkers of Exposure – FAS-EX	Y		
Table 15.2.3.3.1.1	Sensitivity Analysis of Biomarkers of Exposure Including LLOQ Values in Denominator – FAS-EX			
Table 15.2.3.3.2	Secondary Analysis of Biomarkers of Exposure – PP Population			
Table 15.2.3.3.3	Secondary Analysis of Biomarkers of Exposure – FAS-AR			
Table 15.2.4.1.1	Descriptive Statistics of Smokers' Health Profile - FAS-EX			
Table 15.2.4.1.1.1	Descriptive Statistics of Smokers' Health Profile by Sex- FAS-EX			
Table 15.2.4.1.1.2	Descriptive Statistics of Smokers' Health Profile by Consumption Level - FAS-EX			
Table 15.2.4.1.2	Descriptive Statistics of Smokers' Health Profile – PP Population			
Table 15.2.4.1.3	Descriptive Statistics of Smokers' Health Profile – FAS-AR			

Table No.	Title	Topline (Y/N)	Safety (Y/N)	Clinical Trial.gov (Y/N)
Table 15.2.4.2.1	Descriptive Statistics of Biomarkers of Exposure - FAS-EX			
Table 15.2.4.2.2	Descriptive Statistics of Biomarkers of Exposure – PP Population			
Table 15.2.4.2.3	Descriptive Statistics of Biomarkers of Exposure - FAS-AR			
Table 15.2.4.3.1	Descriptive Statistics of Neq, Plasma Nicotine and Cotinine Concentrations – FAS-EX			
Table 15.2.4.3.2	Descriptive Statistics of Neq, Plasma Nicotine and Cotinine Concentrations – PP Population			
Table 15.2.4.3.3	Descriptive Statistics of Neq, Plasma Nicotine and Cotinine Concentrations – FAS-AR			
Table 15.2.4.4.1	Analysis of Neq, Plasma Nicotine and Cotinine Concentrations – FAS-EX			
Table 15.2.4.4.1.1	Sensitivity Analysis of Neq Including LLOQ Values in Denominator – FAS-EX			
Table 15.2.4.4.2	Analysis of Neq, Plasma Nicotine and Cotinine Concentrations – PP Population			

Table No.	Title	Topline (Y/N)	Safety (Y/N)	Clinical Trial.gov (Y/N)
Table 15.2.4.4.3	Analysis of Neq, Plasma Nicotine and Cotinine Concentrations – FAS-AR			
Table 15.2.4.5.1	Descriptive Statistics of Additional Lung Function Markers - FAS-EX			
Table 15.2.4.5.2	Descriptive Statistics of Additional Lung Function Markers – PP Population			
Table 15.2.4.5.3	Descriptive Statistics of Additional Lung Function Markers – FAS-AR			
Table 15.2.4.6.1	Analysis of Additional Lung Function Markers – FAS-EX	Y		
Table 15.2.4.6.2	Analysis of Additional Lung Function Markers – PP Population			
Table 15.2.4.6.3	Analysis of Additional Lung Function Markers – FAS-AR			
Table 15.2.4.7.1	Descriptive Statistics of Additional Cardiovascular Disease Markers by Product Use Pattern - FAS-EX			
Table 15.2.4.7.2	Descriptive Statistics of Additional Cardiovascular Disease Markers – PP Population			
Table 15.2.4.7.3	Descriptive Statistics of Additional Cardiovascular Disease Markers			

Table No.	Title	Topline (Y/N)	Safety (Y/N)	Clinical Trial.gov (Y/N)
	– FAS-AR			
Table 15.2.4.8.1	Analysis of Additional Cardiovascular Disease Markers – FAS-EX	Y		
Table 15.2.4.8.1.1	Sensitivity Analysis of Additional Cardiovascular Disease Markers Including LLOQ Values in Denominator – FAS-EX			
Table 15.2.4.8.2	Analysis of Additional Cardiovascular Disease Markers – PP Population			
Table 15.2.4.8.3	Analysis of Additional Cardiovascular Disease Markers – FAS-AR			
Table 15.2.4.9.1	Summary of Cough Assessment Over Study – FAS-EX			
Table 15.2.4.9.2	Summary of Cough Assessment Over Study – PP Population			
Table 15.2.4.10	Analysis of Proportion of Subjects Reporting Need to Cough Over Study – FAS-EX			
Table 15.2.4.11.1	Descriptive Statistics of MCEQ Subscales – FAS-EX			
Table 15.2.4.11.2	Descriptive Statistics of MCEQ Subscales – PP Population			

Table No.	Title	Topline (Y/N)	Safety (Y/N)	Clinical Trial.gov (Y/N)
Table 15.2.4.12.1	Analysis of MCEQ Subscales – FAS-EX			
Table 15.2.4.12.2	Analysis of MCEQ Subscales – PP Population			
Table 15.2.4.13.1	Descriptive Statistics of FTND Results – FAS-EX			
Table 15.2.4.13.2	Descriptive Statistics of FTND Results – PP Population			
Table 15.2.4.14.1	Descriptive Statistics of Intent to Use THS 2.2 Questionnaire – FAS-EX			
Table 15.2.4.14.2	Descriptive Statistics of Intention to Use THS 2.2 Questionnaire – PP Population			
Table 15.2.4.15	Descriptive Statistics of Distribution of Dual Use over Randomized Exposure Period – FAS-EX			
Table 15.2.4.16	Analysis of Final Propensity Model – FAS-AR			
Table 15.2.4.17	Analysis of Exposure-Response Relationship of Dual Use – FAS-AR			
Table 15.2.5.1	Summary of Product Use Pattern – FAS-EX	Y		

Table No.	Title	Topline (Y/N)	Safety (Y/N)	Clinical Trial.gov (Y/N)
Table 15.2.5.1.1	Summary of Product Use Pattern by Sex - FAS-EX			
Table 15.2.5.1.2	Summary of Product Use Pattern by Consumption Level - FAS-EX			
Table 15.2.5.2	Summary of Product Use Pattern - Safety Population			
Table 15.2.5.3	Summary of Product Use Pattern - FAS-AR	Y		
Table 15.2.5.4	Summary of Detailed Product Use Pattern - FAS-EX			
Table 15.2.6.1	Summary of Adverse Events – Safety Population		Y	
Table 15.2.6.2	Summary of Adverse Events by Product Use Pattern Category – Safety Population	Y	Y	
Table 15.2.6.3	Summary of Adverse Events by System Organ Class and Preferred Term – Safety Population		Y	
Table 15.2.6.3.1	Summary of Monthly Adverse Events by System Organ Class and Preferred Term – Safety Population		Y	
Table 15.2.6.4	Summary of Adverse Events by Product Use Pattern Category, System Organ Class and Preferred Term – Safety Population	Y	Y	

Table No.	Title	Topline (Y/N)	Safety (Y/N)	Clinical Trial.gov (Y/N)
Table 15.2.6.4.1	Summary of Frequent Adverse Events (Incidence >5%) by System Organ Class and Preferred Term and Product Use Category– Safety Population		Y	Y
Table 15.2.6.5	Summary of Adverse Events by System Organ Class, Preferred Term and Relationship to Study Product Exposure and Expectedness – Safety Population		Y	
Table 15.2.6.6	Summary of Adverse Events by Product Use Pattern Category, System Organ Class, Preferred Term and Relationship to Study Product Exposure and Expectedness – Safety Population	Y	Y	
Table 15.2.6.7	Summary of Adverse Events Leading to Study Product Discontinuation, Interruption, or Reduction by System Organ Class and Preferred Term – Safety Population		Y	
Table 15.2.6.8	Summary of Adverse Events Leading to Study Product Discontinuation, Interruption, or Reduction by Product Use Pattern Category, System Organ Class, and Preferred Term – Safety Population		Y	
Table 15.2.6.9	Summary of Adverse Events Related to Study Procedure by System Organ Class and Preferred Term – Safety Population		Y	

Table No.	Title	Topline (Y/N)	Safety (Y/N)	Clinical Trial.gov (Y/N)
Table 15.2.6.10	Summary of Adverse Events Related to Study Procedure by Product Use Pattern Category, System Organ Class and Preferred Term – Safety Population		Y	
Table 15.2.6.11	Summary of Adverse Events by System Organ Class, Preferred Term and Severity – Safety Population		Y	
Table 15.2.6.12	Summary of Adverse Events by Product Use Pattern Category, System Organ Class, Preferred Term and Severity – Safety Population		Y	
Table 15.2.6.13	Summary of Serious Adverse Events by System Organ Class and Preferred Term – Safety Population		Y	
Table 15.2.6.14	Summary of Serious Adverse Events by Product Use Pattern Category, System Organ Class and Preferred Term – Safety Population		Y	
Table 15.2.6.15	Summary of Adverse Events Leading to Study Discontinuation by System Organ Class and Preferred Term – Safety Population		Y	
Table 15.2.6.16	Summary of Adverse Events Leading to Study Discontinuation by Product Use Pattern Category, System Organ Class and Preferred Term – Safety Population		Y	

Table No.	Title	Topline (Y/N)	Safety (Y/N)	Clinical Trial.gov (Y/N)
Table 15.2.6.17	Summary of THS 2.2 Device Events – Safety Population		Y	
Table 15.2.6.18	Summary of Clinical Chemistry Parameters – Safety Population		Y	
Table 15.2.6.19	Summary of Clinical Chemistry Parameters by Product Use Pattern Category – Safety Population		Y	
Table 15.2.6.20	Summary of Hematology Parameters – Safety Population		Y	
Table 15.2.6.21	Summary of Hematology Parameters by Product Use Pattern Category – Safety Population		Y	
Table 15.2.6.22	Summary of Urinalysis Parameters – Safety Population		Y	
Table 15.2.6.23	Summary of Urinalysis Parameters by Product Use Pattern Category – Safety Population		Y	
Table 15.2.6.24.1	Summary of Concomitant Medication by Anatomical Therapeutic Classes (ATC) 1 and 2 – Safety Population		Y	
Table 15.2.6.24.2	Summary of Concomitant Medication by Anatomical Therapeutic Classes (ATC) 1 and 2 and Product Use Pattern Category – Safety Population		Y	

Table No.	Title	Topline (Y/N)	Safety (Y/N)	Clinical Trial.gov (Y/N)
Table 15.2.6.24.3	Summary of Concomitant Medication by Medicinal Product – Safety Population		Y	
Table 15.2.6.24.4	Summary of Concomitant Medication by Medicinal Product and Product Use Pattern Category – Safety Population		Y	
Table 15.2.6.25	Summary of Supine Vital Signs – Safety Population		Y	
Table 15.2.6.26.1	Summary of ECG Results – Safety Population		Y	
Table 15.2.6.26.2	Shift from Baseline of ECG Results by Product Use Pattern Category – Safety Population		Y	
Table 15.2.6.27.1	Summary of Spirometry Results – Safety Population		Y	
Table 15.2.6.27.2	Shift from Baseline of Spirometry by Product Use Pattern Category – Safety Population		Y	
Table 15.2.6.28	Summary of Physical Examination of Body Systems – Safety Population		Y	
Table 15.2.6.29	Summary of Physical Examination of Body Systems by Product Use Pattern Category – Safety Population		Y	

Table No.	Title	Topline (Y/N)	Safety (Y/N)	Clinical Trial.gov (Y/N)
Table 15.2.6.30	Summary of Weight, Waist Circumference and BMI Results – Safety Population		Y	
Table 15.2.6.31	Summary of Weight Results by Product Use Pattern Category – Safety Population		Y	
Table 15.2.6.32	Summary of Cough Assessment Over Study – Safety Population		Y	
Figure 15.1.1.1	Forest Plot of Supportive Analysis of Smokers' Health Profile – FAS-EX			
Figure 15.1.1.2	Forest Plot of Supportive Analysis of Smokers' Health Profile – PP Population.			
Figure 15.1.1.3	Forest Plot of Supportive Analysis of Smokers' Health Profile – FAS-AR			
Figure 15.1.2.1	Histogram of Predicted Propensity Scores of Exposure-Response Relationship – FAS-AR			
Figure 15.1.2.2	Forest Plot of Statistical Analysis of Exposure-Response Relationship – FAS-AR			
Listing 15.3.1.1	Listing of Subject Disposition			

Table No.	Title	Topline (Y/N)	Safety (Y/N)	Clinical Trial.gov (Y/N)
Listing 15.3.1.1.1	Listing of Visits			
Listing 15.3.1.2	Listing of Unmet Inclusion / Exclusion Criteria of Extension Study			
Listing 15.3.1.3	Listing of Questions on Smoking History/Habits			
Listing 15.3.1.4	Listing of Prochaska "Stage of Change" Questionnaire Results			
Listing 15.3.1.5	Listing of Product Preference			
Listing 15.3.1.6	Listing of Urine Pregnancy Results			
Listing 15.3.1.7	Listing of Demographics			
Listing 15.3.1.8	Listing of Assignment to Analysis Sets			
Listing 15.3.1.9	Listing of Medical History and Concomitant Diseases			
Listing 15.3.1.10	Listing of Protocol Deviations			
Listing 15.3.1.11	Listing of Socio-Economic Questionnaire Results			

Table No.	Title	Topline (Y/N)	Safety (Y/N)	Clinical Trial.gov (Y/N)
Listing 15.3.1.12	Listing of Lifestyle Assessment Results			
Listing 15.3.1.13	Listing of Attempt to Quit Smoking			
Listing 15.3.2.1	Listing of Product Usage			
Listing 15.3.2.1.1	Listing of Product Use Categories			
Listing 15.3.2.1.2	Listing of Derived Product Use Summaries			
Listing 15.3.2.2	Listing of THS 2.2 Device Details			
Listing 15.3.2.3	Listing of THS 2.2 Product Accountability			
Listing 15.3.2.4	Listing of Subjects and Observations Excluded from Analysis Populations			
Listing 15.3.3.1	Listing of Urinary Biomarkers			
Listing 15.3.3.2	Listing of Blood, Plasma, Serum, and Exhaled Air Biomarkers			
Listing 15.3.3.3	Listing of Full Lung Function Data and Changes from Baseline			

Table No.	Title	Topline (Y/N)	Safety (Y/N)	Clinical Trial.gov (Y/N)
Listing 15.3.3.3.1	Listing of Not Done Biomarker and Lung Function Parameters			
Listing 15.3.3.4	Listing of Plasma Nicotine and Cotinine Concentrations			
Listing 15.3.3.5	Listing of Cough Assessment Results			
Listing 15.3.4.1	Listing of MCEQ Questionnaire Results			
Listing 15.3.5.1	Listing of FTND Results			
Listing 15.3.5.2	Listing of Intent to Use THS 2.2 Questionnaire Results			
Listing 15.3.6.1	Listing of Adverse Events			
Listing 15.3.6.2	Listing of Serious Adverse Events			
Listing 15.3.6.3	Listing of Adverse Events Leading to Study Discontinuation			
Listing 15.3.6.4	Listing of Prior and Concomitant Medication			
Listing 15.3.6.5	Listing of THS 2.2 Device Events and Malfunctions			

Table No.	Title	Topline (Y/N)	Safety (Y/N)	Clinical Trial.gov (Y/N)
Listing 15.3.6.6	Listing of Clinical Chemistry Data, Shift, Changes from Baseline and CTCAE grades			
Listing 15.3.6.7	Listing of Hematology Data, Shift, Changes from Baseline and CTCAE grades			
Listing 15.3.6.8	Listing of Urinalysis Data, Shift, Changes from Baseline and CTCAE grades			
Listing 15.3.6.9	Listing of Vital Signs Data and Changes from Baseline			
Listing 15.3.6.10	Listing of ECG Data and Changes from Baseline			
Listing 15.3.6.11	Listing of Physical Examination Findings, Shift and Changes from Baseline
